#### 8. TRIAL ASSESSMENTS

## 8.1. Screening assessments

The following assessments should be conducted within 28 days prior to randomisation unless otherwise indicated:

- Physical examination
- Medical history
- ECOG performance status assessment
- Full blood count, urea and electrolytes, amylase and liver function assessment
- Thyroid function assessment
- Serology (HIV, hepatitis B, hepatitis C) (within 12 months prior to randomisation)
- Concomitant medication assessment
- Adverse event assessment (CTCAE v5)
- CT chest abdomen pelvis (CAP) and RECIST v1.1 assessment\*
- QoL sub-study questionnaire (if participating): EORTC QLQ-C30 and EQ-5D-5L

\*The planned site of radiotherapy should not be used for RECIST v1.1 assessment (as either a target or non-target lesion), but measurement of this lesion should be recorded on the dedicated eCRF.

## 8.2. Baseline blood samples

If the participant is taking part in the translational substudy, the following samples should be obtained after randomisation and prior to commencement of trial treatment:

EDTA 10ml x 3, Tempus 3ml and Streck 10ml

#### 8.3. On-treatment assessments

Patients will receive study atezolizumab 1200mg IV three weekly until loss of clinical benefit or unmanageable toxicity. If allocated, radiotherapy should start on the same day as the first cycle of study atezolizumab if possible. For further details see section 9 – Trial Treatment.

The following assessments should be conducted before each three-weekly cycle of atezolizumab (within 72 hrs prior to day 1):

- Physical examination as clinically indicated
- Full blood count, urea and electrolytes, amylase, liver function assessment
- Concomitant medication assessment
- Adverse event assessment (CTCAE v5)

#### Every six weeks:

• Thyroid function (every 6 weeks) - results do not need to be available on day 1

Translational sub-study sample schedule (if participating):

- RT patients only at fraction 4 or 5 EDTA 10ml x 3 and Tempus 3ml
- Week 3 from start of study atezolizumab EDTA 10ml x 3 and Tempus 3ml
- Week 9 from start of study atezolizumab (primary endpoint) EDTA 10ml x 3, Tempus 3ml and Streck 10ml

Quality of life sub-study questionnaire schedule - EORTC QLQ-C30 and EQ-5D-5L (if participating):

- Week 9
- Six months
- Any participants still receiving atezolizumab at 12 months

# 8.4. Primary endpoint assessment (9 weeks after start of study atezolizumab):

In addition to the above assessments:

- CT chest abdomen pelvis (CAP)
- RECIST v1.1 assessment

Primary endpoint assessment should be conducted nine weeks after the start of study treatment, irrespective of any treatment gaps that may have occurred.

Subsequent CT CAP assessments should be conducted every 9 weeks in the first year, then every 12 weeks in the second year until treatment discontinuation. RECIST v1.1 assessments should be conducted on each scan until RECIST v1.1 progression. CT CAP can be conducted according to local practice in line with RECIST imaging recommendations (34). This consists of, as a minimum, use of contiguous slices, with a slice thickness of ≤5mm and IV contrast (unless contraindicated). RECIST assessments should be conducted in accordance with the details in Appendices A1. RECIST and A2. iRECIST.

The planned site of radiotherapy, as specified at randomisation, should not be used for RECIST v1.1 assessment, irrespective of whether or not the participant was allocated to receive radiotherapy. However, please record the measurement for this lesion on the dedicated eCRF.

If atezolizumab is being withheld, CT CAP should still take place at the expected time-points unless the patient has permanently discontinued treatment.

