## 8.5. Treating beyond progression

At the discretion of the treating clinician atezolizumab may be continued past RECIST v1.1 progression until loss of clinical benefit. Patients with rapidly progressive or symptomatic disease with an alternate treatment option should be advised to discontinue trial treatment and have standard of care treatment. See Appendix A4 for guidance on continuing/discontinuing trial treatment and scan assessments required.

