# 8.8. Discontinuation from treatment and post-treatment follow up\*

Participants may discontinue from trial treatment at any time at their own request, or they may be discontinued at the discretion of the Principal Investigator. Reasons for discontinuation may include:

- Disease progression or recurrence
- Loss of clinical benefit
- Unmanageable toxicity
- Pregnancy

Participants who discontinue treatment should continue to have scans at protocol determined intervals until RECIST v1.1. progression or commencement of further systemic treatment. Participants should be followed up:

- For disease status and survival every three months up to two years after study entry and every six months thereafter.
- Patients should be monitored for immune related toxicity for 90 days post treatment completion or until initiation of further systemic treatment, if sooner.

\*Patients with confirmed iRECIST progression (iCPD) would be expected to discontinue study atezolizumab. If it is considered in the patient's best interest to continue treatment this should be discussed with the RE-ARM Chief Investigator (via [contact]) and, once agreed, the patient should continue to be followed up as per iUPD until treatment discontinuation (see Appendix A4).

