#### Footnotes

- 1. Within 28 days before randomisation unless otherwise stated.
- 2. Assessments should be conducted within 72 hours prior to day one of each three-weekly cycle. Following screening, physical examinations should be conducted as clinically indicated.
- 3. To include Hb, Plt, WBC, creatinine, sodium, potassium, ALP, AST or ALT, bilirubin and amylase as a minimum.

RE-ARM protocol IRAS 280335 / CCR5167

4. CT CAP with RECIST v1.1 or iRECIST assessment as appropriate should be conducted at the expected time point irrespective of any delays to atezolizumab administration. The planned site of radiotherapy should not be used for RECIST v1.1 or iRECIST assessment (as either a target or non-target lesion), but measurement of this lesion should be recorded on the dedicated eCRF where required.

- 5. Thyroid function assessments should be conducted every 6 weeks.
- 6. CT CAP with RECIST v1.1 assessment should be conducted every 9 weeks within the first year, every 12 weeks within the second year for those patients continuing treatment. See appendix A4.
- 7. Upon RECIST v1.1 assessment of PD, for patients continuing treatment, CT CAP should be conducted with iRECIST assessment 6 weeks later, then 12 weeks later for those patients without iCPD and continuing treatment. Following this CT CAP with iRECIST assessment should continue every 9 weeks within the first year of study treatment and every 12 weeks within the second year until iCPD or discontinuation of treatment. See appendix A4.
- 8. Assessment of immune related toxicities up to 90 days post treatment completion (prior to initiation of any further treatment).
- 9. Disease status and survival should be assessed every 3 months post atezolizumab discontinuation up to two years after the start of study treatment, then every 6 months thereafter

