#### Secondary endpoints

Objective response rate according to iRECIST and clinical benefit according to RECIST v1.1 will be compared between trial arms as per the primary endpoint. Best response will be tabulated according to trial arm.

Duration of response, time to progression, progression free survival and overall survival will be presented according to trial arm using Kaplan-Meier survival plots and analysed using log-rank tests and Cox proportional hazards models. Rates of progression free and overall survival will be estimated at 12 and 24 months.

Treatment-related toxicity will be presented according to grade and trial arm.

Quality of life data will be analysed using standard algorithms to derive scores and handle missing data according to the questionnaire's scoring manual. The primary outcome measure for patient reported quality of life will be overall quality of life measured by the EORTC QLQ-C30 global health/quality of life subscale score, which will be treated as a continuous variable. Subscale scores will be compared between treatment groups at individual time points, as well as the change from baseline to Week 9 and 6 months, using ANCOVA adjusting for baseline scores. Additional analyses of EORTC QLQ-C30 subscales will dichotomise change in subscale scores from baseline to each follow-up timepoint according to whether or not patients have experienced a deterioration of >10 points, and compared between groups using chi-squared tests or Fisher's exact test, as appropriate. Analyses to account for the longitudinal nature of the data (generalised estimating equations) may also be used. Secondary QoL outcomes of interest include the EORTC QLQ-C30 subcales for physical functioning, role functioning and fatigue, individual domains and utility scores from the EQ-5D-5L.

QoL sub-study patients who are still being treated with atezolizumab at 12 months will be asked to complete the questionnaire at this timepoint. QoL data for this subset of patients will be compared with their baseline QoL data taking into account relevant covariates including other treatments taken, to explore the impact of long term use of atezolizumab on QoL.

Exploratory analyses will be conducted to investigate whether response varies according to site of target lesion. Details will be specified in the Statistical Analysis Plan.

Analyses of efficacy outcomes will be by intention-to-treat; safety analyses will be in the per protocol population.

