## 12.5. Interim analyses and stopping rules

Recruitment will be closely monitored by the Trial Management Group (TMG) with escalation to the independent Trial Steering Committee should it fall below 50% of target after 12 months recruitment (or later). An Independent Data Monitoring Committee (IDMC) will review the accumulating toxicity data approximately 6 months after the first patient is recruited and at least annually in confidence.

Formal interim analysis will be performed when 23 patients per arm have completed the 9 week primary endpoint response assessment in accordance with the group sequential design described in section 12.1. Unless the IDMC advise otherwise, recruitment will continue whilst the interim analysis is carried out, as it is likely that the number of additional patients recruited before the results are known will be small (expected recruited rate is 5 patients per month).

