### A2. iRECIST

### **A2.1 Definitions**

• Evaluable for adverse events.

All patients will be evaluable for adverse event evaluation from the time of their first treatment.

• Evaluable for response.

All patients who have received at least one cycle of therapy and have their disease reevaluated will be considered evaluable for response (exceptions will be those who exhibit objective disease progression prior to the end of cycle 1 who will also be considered evaluable). Patients on therapy for at least this period and who meet the other listed criteria will have their response classified according to the definitions set out below.

Response and progression will be evaluated in this study using the revised international criteria (1.1) proposed by the RECIST (Response Evaluation Criteria in Solid Tumours) committee as well as the modified iRECIST guidelines. Investigators should note the different requirements for confirmatory scans as well as follow up for the two criteria.

See appendix A4 for criteria for continuing treatment past RECIST 1.1 disease progression.

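### Sections 8.4 and 8.8 give opposite instructions on the week-9 CT for a patient who stops treatment early without progression, and the counting rules around that scan are not aligned

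*Protocol*

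**What the plan says.** **The scan.** Section 8.4 sets the timing of the primary assessment: "Primary endpoint assessment should be conducted nine weeks after the start of study treatment, irrespective of any treatment gaps that may have occurred". It ends with a sentence on withheld drug, under which "CT CAP should still take place at the expected time-points unless the patient has permanently discontinued treatment". The schedule in section 8.10 marks a CT at week 9 and none in the column for discontinuation of treatment. Section 8.8 says: "Participants who discontinue treatment should continue to have scans at protocol determined intervals until RECIST v1.1. progression or commencement of further systemic treatment".

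**The counting.** Section 12.1 requires 92 evaluable patients, adds 10% for non-evaluability at 9 weeks to reach 102, and lets the total be adjusted so that 92 evaluable are recruited. Section 12.5 says: "Formal interim analysis will be performed when 23 patients per arm have completed the 9 week primary endpoint response assessment". Appendix A1.6 classes a patient with no imaging at a time point as not evaluable at that time point. Appendix A2.1 says: "All patients who have received at least one cycle of therapy and have their disease reevaluated will be considered evaluable for response", with an exception only for objective progression before the end of cycle 1. Section 12.4 says: "Analyses of efficacy outcomes will be by intention-to-treat", and leaves the definitions of analysis populations to the SAP.

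**The concern.** The primary endpoint is response on one scan at one time. A site that follows the last sentence of 8.4 takes no week-9 CT in a patient who stops for good in the first cycles, for example for toxicity. A site that follows 8.8 takes it. Whether the primary outcome exists would then depend on which section the site read, and no later analysis plan can supply a missing scan. Such stops could differ between arms, because only one arm receives radiotherapy.

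The counting rules decide what the missing scan does to the result. Early losses are plausibly mostly non-responders: under 8.5, patients with rapidly progressive or symptomatic disease who have an alternative option "should be advised to discontinue trial treatment and have standard of care treatment". If unscanned patients left the denominator, the arm with more early failures would look better. The thresholds are low: one extra response decides the interim, and the final boundary is z = 0.68.

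**Working it through.** **1. Which patients the scan conflict reaches.** Take each route by which a patient might have no week-9 CT.

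| Situation before week 9 | 8.4 | 8.8 | Conflict? |
|---|---|---|---|
| Drug withheld or delayed, not stopped for good | CT | not applicable | No |
| Permanent stop, no progression, no new systemic therapy | no CT | CT | Yes |
| Permanent stop, then new systemic therapy | no CT | scans end | No |
| Permanent stop after RECIST v1.1 progression | no CT | scans end | No |
| Death | none possible | none possible | No |

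Only the second row is contradictory. It includes patients who deteriorate clinically without documented progression or new therapy.

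**2. The plan's own figures.** Inputs from section 12.1: 15% v 30%, one-sided, 23 then 46 evaluable per arm, continue if z > 0, positive if final z > 0.68. With X responders per arm, z = (X_E/n − X_C/n) / √(2p(1−p)/n), where p is the pooled proportion. Summing exact binomial probabilities over both stages gives:
- Power at 15% v 30%: 0.795. The normal approximation gives 0.804 to 0.812. The stated 80% is reproduced.
- False-positive rate at 15% v 15%: 0.196.
- Inflation: 92/0.9 = 102.2, and 102 × 0.9 = 91.8.

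The stated power is thus that of 46 evaluable patients per arm; about 10 of the 102 randomised fall outside that count.

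**3. If unscanned patients were excluded.** Assumptions, none of them in the protocol: true response of 15% among all randomised in both arms, every loss a non-responder, and recruitment topped up to 46 evaluable per arm. The evaluable rate is then 0.15/(1 − loss).

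| Loss, control / radiotherapy | Evaluable rates | Exact false-positive rate |
|---|---|---|
| 0 / 0 | 15.0% / 15.0% | 0.196 |
| 10% / 10% | 16.7% / 16.7% | 0.201 |
| 8% / 12% | 16.3% / 17.0% | 0.227 |
| 5% / 15% | 15.8% / 17.6% | 0.271 |
| 5% / 20% | 15.8% / 18.8% | 0.317 |
| 15% / 5% | 17.6% / 15.8% | 0.143 |

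As a cross-check, a simulation held 51 randomised per arm, took the interim after 25 randomised per arm, and split ten expected losses (control/radiotherapy). It gave 0.216 for 5/5, 0.273 for 3/7, 0.305 for 2/8, 0.366 for 0/10 and 0.148 for 8/2. Counting the same patients as non-responders gave about 0.20 in every case.

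**4. If all 102 randomised are kept.** Exact power at 51 per arm with the same boundaries:
- 15% v 30% among all randomised: 0.803 with the interim at 23 per arm, 0.815 at 25.
- 15% v 30% only among the evaluable, with the other 10% counted as non-responders: 0.9 × 15% = 13.5% and 0.9 × 30% = 27%. Power is 0.772 with the interim at 23, 0.785 at 25.

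**The case against.** **The protocol already says intention-to-treat.** A reader might infer that counting evaluable or completed patients contradicts it, so that early failures drop out of the final comparison. The text does not go that far. In 12.1, evaluability sets the sample size; in 12.5, completion times the interim. Neither defines an analysis set, sizing on evaluable patients while analysing by intention-to-treat is common, and populations are left to an SAP not seen here. The not-evaluable label in Appendix A1.6 is a time-point category, and such a patient can still count as a non-responder. This stands. What remains is that the protocol itself fixes the recruitment target, top-up and interim trigger on scanned patients, without tying them to the intention-to-treat denominator.

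**The scan conflict does not explain most early failures.** This also stands, as the first table shows. The group affected is further narrowed by eligibility: stable disease as best response after 3 to 6 cycles, ECOG 0-1, and exclusion of patients expected to live less than 10 weeks.

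**The schedule footnote.** A reader might cite footnote 6, which ends "every 12 weeks within the second year for those patients continuing treatment", against the week-9 scan. It is attached to the column for cycles 5 to 34, so it says nothing about week 9. Footnote 4 requires CT despite dosing delays, but a delay is not a permanent stop. The last sentence of 8.4 and the empty discontinuation column remain in conflict with 8.8.

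**The size is conditional.** Correct: equal losses give almost no inflation, and the bias can reverse. A reader might also infer informative censoring of progression-free survival; that is possible, but it was not calculated and is not part of this point.

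**Conclusion.** The contradiction between 8.4, with the schedule, and 8.8 is real and bears directly on the primary-endpoint scan. It concerns patients who stop permanently before week 9 without RECIST v1.1 progression or new systemic therapy. The protocol gives no figure for how many these will be.

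The denominator issue is secondary: an unresolved inconsistency, not a prescribed exclusion. Its possible effect is a false-positive rate of about 0.14 to 0.32 against 0.196, for assumed loss splits from 15%/5% to 5%/20%. That range requires exclusion, every loss a non-responder, and unequal losses between arms; the only protocol figure is 10% overall. Since the direction cannot be known in advance, the case is for fixing the rule beforehand, not for a predicted bias in favour of radiotherapy.

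**What to change.** 1. Reconcile section 8.4 and the schedule with section 8.8 so that the week-9 outcome CT does not depend on whether the patient is still on treatment. The cost is an amendment, plus scans that 8.8 already calls for.
2. State in 12.1 and 12.4 that the interim and final denominators are all randomised patients. A week-9 assessment missing because of death, progression or clinical deterioration counts as non-response, with evaluable-only as a sensitivity analysis.
3. In 12.1 and 12.5, trigger the interim when the first 23 randomised per arm have reached week 9, early failures included.

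Items 2 and 3 need no material change to the 102 patients. With the interim at 23 per arm, exact power is about 0.80 if 15% and 30% hold among all randomised. If they hold only among evaluable patients it is 0.77, or 0.79 with the interim at 25, against 0.795 as planned. The cost is therefore at most about two percentage points of power: small, but not zero.

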## 8.5. Treating beyond progression

At the discretion of the treating clinician atezolizumab may be continued past RECIST v1.1 progression until loss of clinical benefit. Patients with rapidly progressive or symptomatic disease with an alternate treatment option should be advised to discontinue trial treatment and have standard of care treatment. See Appendix A4 for guidance on continuing/discontinuing trial treatment and scan assessments required.

#### 8.6. Procedure at RECIST v1.1. progression for patients continuing treatment

Participants who continue treatment post RECIST v1.1 progression should continue to be followed up according to the schedule above, with CT scans scheduled as described below (also see Appendix A4).

- A CT CAP for the purposes of iRECIST assessment should be conducted 6 weeks following confirmation of progressive disease according to RECIST v1.1.
- Should the patient continue on treatment following their first iRECIST assessment, subsequent CT CAP should be conducted for further iRECIST assessment at the following intervals:
  - o 12 weeks after first iRECIST assessment
  - Every 9 weeks thereafter in the first year post start of study treatment, then every 12 weeks in the second year
- Translational sub-study samples (if participating): EDTA 10ml x 3, Tempus 3ml and Streck 10ml should be taken at RECIST v1.1 progression. If progression occurs at the primary endpoint bloods only need to be taken once.

## 8.7. Procedure at RECIST v1.1. progression for patients discontinuing treatment

- Physical examination
- Full blood count, urea and electrolytes, amylase, liver function assessment
- Translational sub-study samples (if participating): EDTA 10ml x 3, Tempus 3ml and Streck 10ml should be taken at progression. If progression occurs at the primary endpoint bloods only need to be taken once.

# 8.8. Discontinuation from treatment and post-treatment follow up\*

Participants may discontinue from trial treatment at any time at their own request, or they may be discontinued at the discretion of the Principal Investigator. Reasons for discontinuation may include:

- Disease progression or recurrence
- Loss of clinical benefit
- Unmanageable toxicity
- Pregnancy

Participants who discontinue treatment should continue to have scans at protocol determined intervals until RECIST v1.1. progression or commencement of further systemic treatment. Participants should be followed up:

- For disease status and survival every three months up to two years after study entry and every six months thereafter.
- Patients should be monitored for immune related toxicity for 90 days post treatment completion or until initiation of further systemic treatment, if sooner.

\*Patients with confirmed iRECIST progression (iCPD) would be expected to discontinue study atezolizumab. If it is considered in the patient's best interest to continue treatment this should be discussed with the RE-ARM Chief Investigator (via [contact]) and, once agreed, the patient should continue to be followed up as per iUPD until treatment discontinuation (see Appendix A4).

